3.9.5. Columbia-Suicide Severity Rating Scale (C-SSRS)

The C-SSRS is a questionnaire used to measure the presence and intensity of suicidal ideation and behavior.

Suicidal behavior and suicidal ideation will be summarized descriptively. The number of subjects with suicidal ideation and suicidal behavior during the double-blind treatment period will be summarized by treatment group when applicable.

Supportive tabular display of subjects with all values will be provided, including subject ID number, treatment group, visit number, intensity of suicidal ideation, suicidal behavior type, and lethality of suicidal behavior.

Table 8: C-SSRS Categories for Analysis

Category	C-SSRS Item response is “YES”
Suicidal behavior	Preparatory acts or behavior Aborted attempt Interrupted attempt Actual attempt Complete suicide
Suicidal ideation	Wish to be dead Non-specific active suicidal thoughts Active suicidal ideation with any methods (not plan) without intent to act Active suicidal ideation with some intent to act, without specific plan Active suicidal ideation with specific plan and intent

3.10. Pharmacokinetic/ Pharmacodynamic Data Analysis

Subject listings for the PK sampling time and concentrations of olanzapine, samidorphan, and metabolites of interest will be provided. PK data obtained from plasma samples collected in this study may be included in a subsequent population PK analysis or other post-hoc analyses conducted outside the scope of this SAP.

4. INTERIM ANALYSIS

No interim analysis is planned for this study.

5. CHANGES IN CONDUCT OR PLANNED ANALYSES FROM THE PROTOCOL

Changes have being made to the analyses specified in the [Protocol](#)¹ Section 14.4 to include the region (US vs. non-US) as a factor in the analysis model for all the relevant efficacy endpoints as described above.

6. DEFINITIONS AND CONVENTIONS FOR HANDLING OF THE DATA

Dataset specifications will be provided in a separate document.

6.1. Analysis Visit Windows

Scheduled analysis visits are visits at scheduled timepoints as specified in the protocol ([Table 1 Schedule of Visits and Assessments](#)).

Scheduled analysis visits during the study period will be the same as the nominal visits collected in eCRF. There will be one valid value of assessment kept for each scheduled analysis visit in summary/analysis statistics.

Unscheduled visits are visits with data not collected on the scheduled time point. Unscheduled visits will not be used for by-visit summary/analysis statistics unless specified otherwise.

All unscheduled visits will be included as collected in eCRF in listings.

Visit Day is calculated as (visit date) – (date of the first dose of study drug) +1.

Last postbaseline values are defined as the last valid postbaseline values collected for each subject during the double-blind treatment period.

Any post-baseline values are defined as any valid values collected from scheduled visits if applicable.

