**Table 1: Schedule of Visits and Assessments (Continued)**

Period	Screening	Double-Blind Treatment Period					Follow-Up 
Visit Number	1	2	3	4	5	6	7
Study Day	-10 to -1	1	8	15	22 	29/ET 	43 
Concomitant Medication Review	X	X	X	X	X	X	X
Columbia-Suicide Severity Rating Scale (C-SSRS) 	X	X 	X	X	X	X	X
Abnormal Movement Scales 		X 	X	X	X	X	X
Positive and Negative Syndrome Scale (PANSS) 	X	X 	X	X	X	X	
Modified Overt Aggression Scale 		X	X	X	X 	X 	
Clinical Global Impression – Severity (CGI-S)	X 	X	X	X	X	X	
Clinical Global Impression – Improvement (CGI-I)			X	X	X	X	
Informed Consent for ALK3831-A306						X 	
Emergency treatment card 		X				X	
Admission to Inpatient Unit 	X						
Discharge from Inpatient Unit 				X	X	X	
Study Drug Dispensation 		X	X	X	X		
Study Drug Return and Adherence Review			X	X	X	X	

 Follow-up Visit (V7) is not required for subjects who enroll in ALK3831-A306 A visit window of ±2 days (anchored to Day 1) is allowed Predose Full physical exam at screening; brief physical exam at all subsequent time points.

-  Urine drug screen via dipstick at screening and prior to randomization on Day 1. Drug screen at Visits 5 and 6 applies to outpatient subjects only. Urine drug screen includes opiates, phencyclidine (PCP), amphetamine/methamphetamine, and cocaine.
-  For outpatient subjects only
-  Serology testing includes anti-human immunodeficiency virus (HIV) antibody, hepatitis B surface antigen, and anti-hepatitis C antibody.
-  Subjects must fast (no food or drink except water) for at least 8 hours before lab draws. Lab draws are to be conducted in the morning for all specified visits.
-  One PK sample will be collected at the specified visits to measure plasma levels of olanzapine, samidorphan, and metabolites of interest
-  Vital signs include orthostatic blood pressure and heart rate, respiratory rate, and oral body temperature. Blood pressure, pulse rate, and respiratory rate will be taken after the subject has been supine for 5 minutes and once again after the subject has stood for 2 minutes.

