### **8.3.9.3. Safety Assessments**

#### **8.3.9.3.1. Abnormal Movement Rating Scales**

The PI or designee will complete the following abnormal movement rating scales: The Abnormal Involuntary Movement Scale (AIMS, [Appendix E](#)) ([Guy 1976](#)), the Barnes Akathisia Rating Scale (BARS, [Appendix F](#)) ([Barnes 1989](#)), and the Simpson-Angus Scale (SAS, [Appendix G](#)) ([Simpson and Angus 1970](#)) at the time points specified in [Table 1](#).

After administration of the first dose of study drug, if a subject complains of extrapyramidal symptoms on a day when abnormal movement scale assessments are not scheduled, an unscheduled abnormal movement assessment should be performed.

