#### **8.4.3. Permitted Therapy**

Permissible medications to treat extrapyramidal symptoms may include benzodiazepines, antihistamines, and anticholinergics. Continuous use of these medications should be avoided if possible and they should only be given to the patient after all study assessments have been performed. While insomnia may be treated with a variety of agents, short half-life benzodiazepines should be utilized due to the potential for lingering effects on daytime functioning and study assessments (eg, triazolam). Non-benzodiazepine medication may be used to treat insomnia (eg, zolpidem, eszopiclone). Treatment of agitation and/ or anxiety with benzodiazepines is permissible. However, doses should be restricted to no more than a 2 mg lorazepam equivalent per day and should be kept as stable as possible throughout study so as not to interfere with daytime functioning and study assessments.

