3.9.4. Abnormal Movement Scales

Extra pyramidal symptoms (EPS) will be evaluated as AEs and also assessed by abnormal movement scales. Abnormal movement scales will include the following: Abnormal Involuntary Movement Scale (AIMS), Barnes Akathisia Rating Scale (BARS), and Simpson-Angus Scale (SAS).

For all abnormal movement scales, total scores and subscale scores will be summarized by treatment group at each visit for the absolute value and for changes from baseline.

Number and percentage of subjects meeting the criteria for treatment emergent Parkinsonism (SAS total score >3), for treatment emergent akathisia (BARS global clinical assessment of akathisia score ≥ 2), for treatment emergent dyskinesia (AIMS score ≥ 3 on any of the first 7

items, or a score ≥ 2 on two or more of any of the first 7 items) at any postbaseline visit will be summarized by treatment group.

A listing will be provided for every abnormal movement scale. Listing for treatment emergent EPS will be provided.

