7. GENERAL STATISTICAL METHODOLOGY

In general, summary statistics (n, mean, standard deviation [SD], median, minimum, and maximum for continuous variables, and number and percentage of subjects in each category for categorical variables) will be provided by treatment group. All summary tables will be based on observed data, and missing values will not be imputed unless otherwise indicated. Measurements collected from unscheduled visits or repeated assessments will not be included in the by-visit summary tables or figures, but will be included in the analyses for the PCS postbaseline values, and subject listings. Source data for the summary tables and statistical analyses will be presented as subject data listings.

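### Read literally, the SAP leaves complaint-triggered AIMS, BARS and SAS ratings out of the treatment-emergent EPS rates, and its rules on unscheduled values conflict for PCS counts

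*SAP*

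**What the plan says.** - **Trigger.** Protocol 8.3.9.3.1 provides that, where an EPS complaint arises after the first dose on a day without a planned rating, "an unscheduled abnormal movement assessment should be performed". The wording is should, not must.
- **Schedule.** Protocol Table 1 places the three scales predose on Day 1, then on Days 8, 15, 22 and 29, and at the Day 43 follow-up.
- **EPS rates.** SAP 3.9.4 sets cut-offs for parkinsonism (SAS total above 3), akathisia (BARS global score of 2 or more) and dyskinesia (AIMS item rules). Subjects reaching each cut-off "at any postbaseline visit will be summarized by treatment group".
- **Definition.** SAP 6.1: "Any post-baseline values are defined as any valid values collected from scheduled visits if applicable". It also keeps unscheduled visits out of by-visit statistics unless otherwise specified, and sends them to listings.
- **Exception.** SAP 7 keeps unscheduled and repeat measurements out of by-visit tables and figures, yet says they "will be included in the analyses for the PCS postbaseline values, and subject listings".
- **Scope of PCS.** Protocol 14.6 ties PCS to laboratory values, vital signs, weight and ECG. SAP Tables 1, 5, 6 and 7 give criteria for those only.
- **Laboratory summaries.** SAP 3.9.2 restricts the summaries to scheduled laboratory parameters and lists the rest, in the same section that defines the laboratory PCS counts.
- **Treatment of symptoms.** Protocol 8.4.3: "Permissible medications to treat extrapyramidal symptoms may include benzodiazepines, antihistamines, and anticholinergics".

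**The concern.** A rating done because the subject has just complained is a natural place to find a positive score. If it does not count, an episode that starts after one weekly visit and has settled or been treated by the next can be rated, recorded and still be absent from the parkinsonism, akathisia or dyskinesia rate. These rates are pre-specified summaries under the safety and tolerability objective, and AE reporting does not apply the SAS, BARS and AIMS cut-offs. SAP section 5, which lists changes from the protocol, does not present the omission as deliberate.

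The PCS conflict has a different consequence: two programmers following different sections of the same SAP could produce different PCS counts from the same data.

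**Working it through.** The plan states no figure on this point, so there is none to reproduce. The check is a cross-reading followed by simple arithmetic.

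**1. Rule chain.** SAP 3.9.4 uses an any-post-baseline-visit criterion. SAP 6.1 limits any post-baseline values to scheduled visits. SAP 7 makes an exception for PCS analyses and listings. No movement scale has a PCS criterion, and SAP 3.9.4 does not call its cut-offs PCS. No sentence brings the unscheduled ratings into the EPS rates.

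**2. Direction within an arm.** Let S be the subjects positive at one or more scheduled ratings and U those positive at one or more unscheduled ratings.
- Scheduled-only count = |S|
- Count using all ratings = |S| + |U not in S|, which is at least |S|

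With the denominator fixed, leaving out U can only lower the rate. SAP 3.9.4 states no denominator; I take the treated subjects in the arm.

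**3. Days affected.** From Day 2 to Day 29 there are 28 days, of which 4 (Days 8, 15, 22, 29) carry a scheduled rating. 28 - 4 = 24, and 24/28 = 86%. These are nominal days. The figure is a share of days on which a complaint would trigger a rating outside the schedule, not a share of episodes missed.

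**4. Size, illustration only.** Let p be the share of an arm positive at an unscheduled rating, and s the share of those also positive at a scheduled one. The rate rises by p(1 - s) when unscheduled ratings count. Both inputs are assumed. With 130 subjects per arm:

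| p | s | p(1 - s) | Subjects of 130 |
|---|---|---|---|
| 2% | 75% | 0.5 points | 0.7 |
| 2% | 50% | 1.0 points | 1.3 |
| 5% | 50% | 2.5 points | 3.2 |
| 10% | 50% | 5.0 points | 6.5 |
| 10% | 25% | 7.5 points | 9.8 |

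The width of this range shows that the documents do not fix the size.

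**5. Between arms.** The all-ratings difference minus the scheduled-only difference is p_A(1 - s_A) - p_P(1 - s_P), with A for active and P for placebo.
- Same p and s in both arms: 0.
- p_A = 5%, p_P = 2%, s = 50% in both: 2.5 - 1.0 = 1.5 points, so the scheduled-only difference is too small.
- p_A = 2%, p_P = 5%, s = 50% in both: 1.0 - 2.5 = -1.5 points, so it is too large.

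The sign is therefore not determined by the text.

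**6. PCS counts.** Laboratory and weight PCS counts (SAP 3.9.2 and 3.9.3.2) are worded as occurring at any post-baseline visit. Under 6.1 that means scheduled values only, and 3.9.2 points the same way for laboratory data. SAP 7 says unscheduled values are included. Both cannot hold.

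**The case against.** The strongest reply is that exclusion is not the only reading. SAP 3.9.4 speaks of a visit, while 6.1 defines values and adds the qualifier if applicable, which it does not explain. SAP 6.1 itself calls unscheduled assessments visits, and 6.1 and 7 bar them expressly only from by-visit output, which an any-visit incidence is not. Dataset and programming specifications are separate documents and might settle it. This stands in part: a lenient reading exists. It does not remove the problem, because the one sentence that defines the any-post-baseline term points to scheduled visits and nothing in the SAP overrides it for EPS.

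Second, EPS is also evaluated as adverse events. These are monitored continuously, and SAP 3.9.1.1 summarizes EPS TEAEs by arm. A listing of treatment-emergent EPS is planned too. This stands in full: the gap is confined to the scale-based rates.

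Third, scheduled ratings give every subject still in the study the same planned looks, whereas complaint-triggered ratings add looks for those who complain. Counting scheduled ratings only is a defensible choice if it is stated. This is why both rates should be shown.

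Fourth, masking by treatment is uncertain. Protocol 8.4.3 discourages continuous use of EPS medication and places it after study assessments. That weakens the case that a later scheduled score is suppressed, but it also makes it likely that the triggered rating catches the untreated episode.

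A reader might go further and infer that the EPS rates are materially biased and that the active-placebo difference is understated. The documents do not support that. They give no EPS incidence, duration or complaint rate by arm, and they do not rank the movement scales above the other safety measures.

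**Conclusion.** The point holds as a literal reading of the SAP, with moderate confidence because of the undefined qualifier in 6.1. Complaint-triggered AIMS, BARS and SAS ratings do not enter the treatment-emergent parkinsonism, akathisia and dyskinesia rates. A subject positive only at such a rating is missed there but remains in the listings, and the event is still open to capture as an EPS TEAE. Given a fixed denominator, the within-arm rate can only be understated. The amount cannot be estimated: the 0.5 to 7.5 points above follow from assumed inputs. It is tempting to assume an episode length and compute the share that weekly visits would miss, but that share merely restates the chosen length. Any effect on the active-placebo difference depends on how between-visit complaints differ by arm and can go either way.

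The conflict of SAP 6.1 and 3.9.2 with SAP 7 over PCS counts is independent of all this and needs reconciling whatever the EPS rates turn out to be. Neither issue touches the primary efficacy conclusion.

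**What to change.** - **SAP 3.9.4:** state that the categorical EPS rates use all double-blind post-baseline ratings, scheduled and unscheduled. Show the scheduled-only rate as a separate row, because triggered ratings give subjects unequal numbers of looks. Name the denominator.
- **SAP 6.1:** redefine the any-post-baseline term to include unscheduled values for PCS and treatment-emergent categorical analyses, and remove or explain the open qualifier.
- **SAP 3.9.2:** limit the scheduled-only sentence to by-visit summaries, so that it agrees with SAP 7.
- **By-visit summaries:** leave them on scheduled visits.

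The cost is a few sentences, one programming flag and one extra table row. The data are already to be collected. The headline EPS rates will be the same or higher and will depend partly on complaint behaviour, which the separate row makes visible. Protocol 14.2 has the SAP finalized before database lock and unblinding, so the choice should be fixed by then.

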6.2. Handling of Partial Dates of Concomitant Medication

Partial start dates of prior and concomitant medications will be assumed to be the earliest possible date consistent with the partial date. Partial stop dates of prior and concomitant medications will be assumed to be the latest possible date consistent with the partial date. In the case of completely missing stop date, medication will be assumed to be ongoing.

6.3. Handling of Safety Data

All efforts should be made to obtain the missing information from the investigator. For C-SSRS, vital signs, laboratory testing (chemistry, hematology, urinalysis), and 12-lead ECGs, only observed data will be used for analyses, and missing data will not be imputed.

7. GENERAL STATISTICAL METHODOLOGY

In general, summary statistics (n, mean, standard deviation [SD], median, minimum, and maximum for continuous variables, and number and percentage of subjects in each category for categorical variables) will be provided by treatment group. All summary tables will be based on observed data, and missing values will not be imputed unless otherwise indicated. Measurements collected from unscheduled visits or repeated assessments will not be included in the by-visit summary tables or figures, but will be included in the analyses for the PCS postbaseline values, and subject listings. Source data for the summary tables and statistical analyses will be presented as subject data listings.

7.1. Reporting Precision

Summary statistics will be presented to the following degree of precision, unless otherwise specified:

Table 9: Degree of Precision

Statistics	Degree of Precision
Mean, Median, Confidence limit boundaries	One more than the raw data, up to 3 decimal places.
Standard deviation, Standard error	One more than the mean, up to 3 decimal places.
Minimum, Maximum	The same as the raw data, up to 2 decimal places.
p-value	Rounded to 3 decimal places and therefore presented as 0.xxx; p-values smaller than 0.001 as '<0.001'; p-values greater than 0.999 as '>0.999'.
Percentage	One decimal place. A percentage of 100% will be reported as 100%. Percentages of zero will be reported as 0.

Fractional numeric values will be presented with a zero to the left of the decimal point (for example, 0.12-0.30).

For weight, height, and BMI, one decimal place will be used for summary statistics.

8. PROGRAMMING SPECIFICATIONS

Programming specifications will be provided in a separate document.

9. MOCK TABLES, LISTINGS AND FIGURES (TLFS)

Mock-up tables and listings will be provided in a separate document.

